Analytic Plan:	SPSS version 23.0 will be used to conduct all quantitative statistical analyses. Participants (N=50) will be randomly assigned to the culturally competent communication intervention group or PLAN (n=25) or the control group (n=25). They will then complete measures of engagement in ACP post-intervention. Preliminary analyses will utilize t-tests to compare the two groups on baseline characteristics (e.g., education, age). Using a criterion of $p < .10$, any variables that are different among the groups will be included in the final logistic regression models as potential confounders. Five separate logistic regression models will be run in which ACP outcomes (end-of-life care discussions with family and providers; and the completion of advance directives DNR, health care proxy, and living will) will be predicted by the group variable (intervention vs. control). The statistical power of the proposed logistic regressions to detect a minimum odds ratio of 2.0 for dichotomous outcome measures of ACP, for a two-tailed test with power $(1 - \beta)$ equal to 0.80, and $\alpha = 0.05$, requires a sample size of 113. Our proposed sample size of n=50 will be underpowered if the effect size is small but adequately powered if it is large.

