6.2.5 Record Retention

Essential documents are those documents that individually and collectively permit evaluation of the study and quality of the data produced. After completion of the study, all documents and data relating to the study will be kept in an orderly manner by the Investigator in a secure study file. Essential documents should be retained for 2 years after the final marketing approval in an ICH region or for at least 2 years since the discontinuation of clinical development of the IP. In addition, all subject medical records and other source documentation will be kept for the maximum time permitted by the hospital, institution, or medical practice.

7. Statistical Considerations

Participants (N=50) will be randomly assigned to the intervention group (n=25) or the control group (n=25). They will then complete measures of engagement in ACP post-intervention. Feasibility and acceptability will be examined with frequency and descriptive statistics (i.e., mean, median, standard deviation, range) for enrollment rates, number of sessions completed, number of weeks required to complete the intervention, and Likert-scale items assessing satisfaction with the intervention and perceived helpfulness. Because this is a pilot study, in accordance with published standards for pilot feasibility clinical trials,⁵⁴ inferential statistics on measures of feasibility ($\geq 70\%$ intervention completion rates) and acceptability ($\geq 70\%$ rate it as "helpful" or "very helpful") are not recommended. Rather, we will examine the average rates of completion

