as well as satisfaction and helpfulness ratings to determine feasibility and acceptability based on those values being equal to or greater than 70%. We will also conduct qualitative analyses on the open-ended questions related to helpfulness. Thematic analysis using an iterative process will be conducted for all qualitative analyses.⁵⁵⁻⁵⁹ A coding scheme and codebook will be created to analyze transcripts of the responses to the open-ended question. Transcripts will be coded separately by two individual coders for manifest (e.g., frequencies) and latent (e.g., underlying themes) variables. If discrepancies occur, a third coder will resolve these conflicts. Interviews will continue until thematic saturation is achieved.^{60,61} Based on our prior field testing of interventions with patients with advanced illness, we anticipate reaching saturation with n=10 participants. Thus, n=25 in the experimental condition should be well powered to reach thematic saturation.

To examine potential efficacy, preliminary analyses will utilize t-tests to compare the two groups on baseline characteristics (e.g., education, age). Using a criterion of $p < .10$, any variables that are different among the groups will be included in the final logistic regression models as potential confounders. To test the study aim, five separate logistic regression models will be run in which ACP outcomes (yes/no to EOL discussions with family and providers; and the completion of advance directives DNR, health care proxy, and living will) will be predicted by the group variable (CCC intervention vs. control). The statistical power of the proposed logistic regressions to detect a minimum odds ratio of 2.0 for dichotomous outcome measures of ACP, for a two-tailed test with power $(1 - \beta)$ equal to 0.80, and $\alpha = 0.05$, requires a sample size of 113. Our proposed sample size of n=50 will be underpowered if the effect size is small but adequately powered if it is large. However, this study is a preliminary pilot and the main focus and goal of this is to determine feasibility, acceptability, and to provide preliminary data to inform a fully-powered RCT in future research (R01 submission).

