7.1 Randomization. We will utilize stratified randomization at the level of each site to ensure balance across the interventional and control groups at the level of each site. To randomize, we will employ a random number generator to randomize participants to study arms at the level of each site. To ensure randomization was effective, separately for each binary outcome, we will perform a two-sample proportions test to test if the rate of outcomes is significantly different between intervention and control groups. Separately for each continuous outcome, we will perform a two-sample unpaired t-test or unpaired Wilcoxon test (as appropriate) to test if the rate of outcomes is significantly different between intervention and control groups.

7.2 Missing data. To reduce missing data, study staff will conduct interviews rather than relying on written self-reports. This approach has been used previously in our prior work to help reduce data that is missing due to patients accidentally overlooking or missing items or requiring clarification of certain terms (e.g., what is an advance directive). Due notice is taken to ensure that patients know that they are free to skip items they prefer not to answer.

8. Adverse Event Reporting Requirements

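### The 113 patients stated for an odds ratio of 2.0 is too low: with a 1:1 group variable the total is at least about 260 to 290

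*Combined protocol and SAP*

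**What the plan says.** Section 7 plans five logistic regressions: end-of-life discussions with family and with providers, and completion of a DNR order, a health care proxy and a living will. Each outcome "will be predicted by the group variable (CCC intervention vs. control"). Allocation is 25 to 25.

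The power statement concerns the ability "to detect a minimum odds ratio of 2.0 for dichotomous outcome measures of ACP", two-tailed, with power 0.80 and alpha 0.05, and says that this "requires a sample size of 113. Our proposed sample size of n=50 will be underpowered if the effect size is small". The second of these sentences thus sets 113 against the planned total of 50, and it ends "but adequately powered if it is large". The Analytic Plan row of the Protocol Summary repeats the same statement. Neither place gives a control-group rate, a formula, a software routine or an odds ratio for a large effect.

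Section 7 adds that the trial is a preliminary pilot, mainly about feasibility and acceptability, and is meant "to provide preliminary data to inform a fully-powered RCT in future research".

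**The concern.** An odds ratio of 2.0 between two equal groups is a modest difference: at best about 17 percentage points (41% against 59%). A comparison of that size normally needs well over 100 patients per arm, so a total of 113 looked too small whatever control rate was assumed.

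This is the only power statement for the efficacy models. It appears twice, and potential efficacy is part of the primary objective. A requirement that is too low makes the pilot seem closer to adequate than it is. It also leaves a poor reference figure on record for planning the later trial.

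**Working it through.** **Inputs.** From Section 7: odds ratio 2.0, two-sided alpha 0.05 (z = 1.960), power 0.80 (z = 0.842), binary group variable, 1:1 allocation. No control rate p₁ is given, so every rate was searched and the most favourable one used. The intervention rate is p₂ = 2p₁/(1 − p₁ + 2p₁). The calculation is unadjusted, with no loss to follow-up and no multiplicity correction.

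**Trying to reproduce 113.** No control rate gives 113 under the stated inputs. Figures near it appear only if an input is changed:

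- A continuous covariate with odds ratio 2.0 per standard deviation, at an event rate of 17.5%: (1.960 + 0.842)²/(0.175 × 0.825 × (ln 2)²) ≈ 113.2. The plan's predictor is a two-level group.
- A one-sided test with 113 read as per arm (for example 111 per arm at a 30% control rate). The plan says two-tailed.
- A relative risk of 2.0, 25% against 50%: 116 in total. That is an odds ratio of 3.0.

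The documents do not show where 113 came from.

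**Smallest sample size.** Each formula is minimised at p₁ = 0.414, p₂ = 0.586. There the difference is d = 0.1716, p₁(1−p₁) = p₂(1−p₂) = 0.2426, and (1.960 + 0.842)² = 7.849.

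| Formula | Per arm | Total, equal arms |
|---|---|---|
| Unpooled: 7.849 × (2 × 0.2426)/d² | 129.4 | 260 |
| Arcsine: 2 × 7.849/0.3449² | 132.0 | 264 |
| Pooled: (1.960√0.5 + 0.842√0.4853)²/d² | 132.1 | 266 |
| Wald, log odds ratio: 7.849 × (2/0.2426)/(ln 2)² | 134.7 | 270 |
| Pooled with continuity correction | 143.6 | 288 |

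This is a floor. By the pooled formula the total is 300 or less only for control rates of about 26–59%. Section 2 (Background and Significance) quotes 32% for end-of-life discussions and 9% for living wills among Latinos. The plan does not adopt these as control rates. Used only as illustration, they give 276–282 and 618–636 in total (pooled to Wald).

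**Power at 113.** By the pooled normal approximation with 56.5 per arm, power is Φ[(√56.5 × 0.1716 − 1.386)/0.6966] = Φ(−0.138) = 44.5%. The plan names no test for the logistic models, so exact enumeration of all 2×2 tables was done for four tests, again at each test's most favourable control rate:

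| | Fisher | Wald | Score | Likelihood ratio |
|---|---|---|---|---|
| Power for OR 2.0, N = 113 | 40.4% | 47.9% | 47.9% | 47.9% |
| Power for OR 2.0, N = 226 (113 per arm) | 70.1% | 74.6% | 74.6% | 74.6% |
| Power for OR 2.0, N = 50 | 17.9% | 22.1% | 26.6% | 26.6% |
| Smallest OR with 80% power, N = 50 | 5.66 | 5.28 | 4.73 | 4.73 |
| Largest type I error, N = 50 | 3.3% | 5.1% | 6.5% | 8.8% |

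**What a large effect means at n=50.** The smallest detectable odds ratios in the table occur at control rates of about 30–37%. Best-case power at n=50 is 41–53% for an odds ratio of 3 and 61–71% for an odds ratio of 4. Rare outcomes do worse: at an assumed 9% control rate, power for an odds ratio of 2.0 is 3.8–14.9%, depending on the test.

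**Size of the misstatement.** 260/113 = 2.3. 50/113 = 44%, whereas 50/260 = 19%.

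**The case against.** The strongest reply is that the figure decides nothing. N=50 was not derived from 113, the 70% benchmarks for feasibility and acceptability do not use it, and Section 7 already tells the reader that n=50 lacks power for small effects and that efficacy is left to a later trial. The correction changes how large the shortfall is, not whether there is one. Nor does the plan say that the later trial will be sized at 113, so harm to its planning is possible rather than shown. All of this stands, and it limits the importance of the point.

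Two technical objections also have some force. First, at 25 per arm the score and likelihood-ratio tests exceed the nominal 5% level, so the favourable ends of the n=50 ranges (27% power, odds ratio 4.7) flatter the design. They serve here as upper bounds, so the conclusion is not weakened. Second, the planned models may include baseline covariates, and the calculation is unadjusted. If 2.0 is a marginal odds ratio, prognostic covariates could lower the requirement somewhat. However, covariates picked because the groups differ at p < .10 need not be prognostic, and nothing in the plan suggests a reduction from about 260 to 113.

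Reading 113 as per arm does not help. The text sets it against a total of 50, and 226 patients would still fall short of 80% power.

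**Conclusion.** The stated 113 is an arithmetic error. Under the plan's own inputs the total is at least about 260–290, which is 2.3 times the stated figure or more, and 113 patients give at most 40–48% power. This rests on 1:1 allocation, a two-sided 0.05 test and an unadjusted comparison without dropout. It does not depend on a chosen control rate, because the most favourable one was used. The unquantified claim about large effects holds only for odds ratios of about 5 or more. The point should be fixed, but it does not affect enrolment or the feasibility and acceptability aims.

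**What to change.** In Section 7 and in the Analytic Plan row of the Protocol Summary, replace the sentence with 113 and the one after it with text such as:

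> For a 1:1 group variable, an odds ratio of 2.0 (two-sided 0.05, 80% power, unadjusted) needs at least about 260–290 patients in total at the most favourable control rate (about 41%), and more at other rates. With n=50, power for an odds ratio of 2.0 is below about 30% at any control rate (18–27% at best, depending on the test). Power of 80% is reached only for an odds ratio of about 5 or more (4.7–5.7 at the most favourable control rate, depending on the test). Power for rare outcomes is lower still.

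If a single power figure for n=50 is given later, name the test beside it and label any control rate as an assumption. The cost is wording in two places. Enrolment, allocation, endpoints and analyses do not change, though the stated requirement becomes less favourable.

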Recruitment and retention. We will recruit advanced cancer patients from three sites: FHCC, UT Southwestern, and Confluence Health. To maximize recruitment rates and ensure timely completion of the proposed study, we will use multiple methods and processes used in our prior (R01-CA106370, PI: [name]) and current work (K07-CA207580, PI: [name]; R21-CA224874, PI: [name]) outlined below. Our team of investigators, most notably [name] (PI), [name] (Co-Investigator), and [name] (Co-Investigator) have a long track record of success recruiting advanced cancer patients to research studies. Sampling and recruitment procedures to be utilized in the present study, as noted, have been used for similar NCI-funded studies (e.g., CwC I, II, and III; PI: [name]; Site PI: [name]). Recruitment across these studies (e.g., R01-CA106370, PI: [name]) have indicated recruitment rates of 70-80% for an advanced cancer patient population with the same eligibility criteria outlined in this application. As such, we project a conservative estimate of 70% of eligible patients. The average number of new advanced cancer patients seen annually at FHCC (based on solid tumors included in the proposed study) is n= 2,405, of whom n=372 identify as Latinx (based on 2019 numbers from formerly Seattle Cancer Care Alliance). Given this projected

patient flow, the allowed year for active recruitment is a highly feasible timeline for recruiting n=50 patients at FHCC.

Although our prior studies have successfully recruited 70% of advanced cancer patients, we acknowledge that recruitment to the present study may pose different and unique challenges. As such, we outline here the specific measures we will take to maximize rates of recruitment and retention to ensure timely and full completion of the study at each site.

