At UTSW, [name] and other providers within the PHHS palliative care clinic will refer potentially eligible patients to UTSW research study members. A Form HH HIPPA supplement and waiver of authorization has been sent and approved by Fred Hutch and UTSW IRB in order to review EMRs to determine eligibility for recruitment purposes. When an eligible patient is identified and confirmed, the UTSW study member will either approach the eligible patient in person, during a clinic visit, or mail out recruitment material, if they are unable to approach the patient in person. If approaching the eligible patient in person, the study member will coordinate with the clinic staff to find an appropriate time to approach the patient. When approaching the patient, the study member, will proceed to describe the study and give the patient a study flyer. If the research study member is unable to meet the patient during their clinic visit, they will mail the patient an envelope containing a study flyer and information sheet. An information sheet is a UTSW form used to provide study information to potential participants and used for guiding the verbal consenting process. Two weeks after mailing out the letters, UTSW study staff will contact the participant over the phone to gauge interest for study participation. A Form HH Waiver of Consent documentation has been sent and approved by Fred Hutch and UTSW IRB in order to waive documentation of consent (signed form) in order to obtain verbal consent.

If the patient is interested after the in person or telephone call approach, the patient will give verbal consent for participation to the UTSW study member. Once verbal consent has been obtained the UTSW research assistants, will notify the Fred Hutch coordinator. The Fred hutch coordinator and social worker will then carry out the rest of the study procedures with the UTSW participants over the phone. Since the Fred Hutch Coordinator and social worker conduct the remaining study procedures, they will mail out the gift cards to participants who

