3.9 Intervention Administration

A total of 50 Latino advanced cancer patients will be enrolled in this study and randomly assigned to the intervention (n=25) or control (n=25) condition. Pre-intervention, patients'

communication goals will be assessed. Then, patient will participate in the intervention or a usual care control condition. After participating in the intervention or control condition, patients' engagement in ACP will be assessed to determine if the intervention improved ACP engagement and planning.

The intervention itself will be administered by a fully trained, licensed social worker via telephone. This interventionist will use a culturally competent communication intervention to "coach" patients in how to be motivated for and to actually engage in ACP, and will be bilingual in Spanish and English.

Patients randomized into the control group will receive usual care. For usual care, patients will engage in standard care with no modifications. Thus, ACP discussions will only occur as they do in usual clinical care (i.e. brought up in clinical encounters).

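### Section 7.1 promises balance at each site but names no restriction on the random draws; as written, stratifying by site adds nothing, and the outcome models leave site out

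*Combined protocol and SAP*

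**What the plan says.** Section 7.1 (Randomization) gives the purpose of stratifying by site as "to ensure balance across the interventional and control groups at the level of each site". The mechanism follows in one sentence: "we will employ a random number generator to randomize participants to study arms at the level of each site". The documents mention no block, block size, minimisation or per-site quota.

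The Protocol Summary and Sections 3.1, 3.9 and 7 all fix the arm sizes; in Section 3.9 patients are "randomly assigned to the intervention (n=25) or control (n=25) condition". Section 3.5 names the strata: "We will recruit advanced cancer patients from three sites: FHCC, UT Southwestern, and Confluence Health". It also shows that they recruit differently. At UTSW the lead collaborator and "other providers within the PHHS palliative care clinic will refer potentially eligible patients", while FHCC screens oncology clinic schedules and Confluence relies on oncologist referral.

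In Section 7 the five logistic models have group as the planned predictor. Any other variable enters only if the arms differ on it at baseline with p < .10.

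**The concern.** Stratification balances arms within a stratum only when something restrains the draws inside it. Independent 1:1 draws made separately at three sites have the same distribution as independent 1:1 draws for all 50 patients, so the site label does no work. The stated purpose then does not follow from the stated method, and neither do the arm sizes.

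Site plausibly matters for these outcomes. Patients reached through a palliative care clinic may already have had more end-of-life discussions or completed more directives than patients reached through oncology clinics, and Section 3.4 deliberately does not exclude prior completion. If one arm happens to receive more of the palliative-clinic patients, the arm difference moves for a reason unrelated to PLAN. The planned models do not adjust for site. The check in Section 7.1 that randomization was effective compares outcomes between arms, not the distribution of sites.

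**Working it through.** **Inputs from the documents.** N = 50, target 25/25, three sites. The 25/25 figure is a design target (50 × 1/2); the plan derives nothing that could be reproduced.

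**Assumptions.** Enrolment per site and background rates by site are not given. I use 17/17/16 as the main split, with 25/15/10, 20/20/10 and 30/10/10 as alternatives, and site gaps of 40 and 20 percentage points.

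**1. Overall split under unrestricted 1:1 draws, Binomial(50, 1/2).**
- P(exactly 25/25) = C(50,25)/2^50 = 0.112.
- P(24 to 26 per arm) = 0.328.
- P(30/20 or worse) = 2 × P(X ≥ 30) = 0.203.

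**2. Split within a site.**
- Site of 10: P(7/3 or worse) = 2 × (120 + 45 + 10 + 1)/1024 = 352/1024 = 0.344.
- Sites of 17/17/16: a site of 17 splits 12/5 or worse with probability 0.143, and a site of 16 splits 12/4 or worse with probability 0.077. P(at least one does) = 1 − (1 − 0.143)² × (1 − 0.077) = 0.32.
- Over the four assumed splits, at least one site is 2:1 or worse in 42-61% of trials.

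**3. Effect on the arm difference.** If one site's background rate is g points above the others, the chance shift is g × (that site's share of the PLAN arm − its share of the control arm). For a site of 17 the share is 17/50 = 0.34, and with unrestricted draws

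SD ≈ g × √[0.34 × 0.66 × (1/25 + 1/25)] = g × 0.134,

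which is 5.4 points at g = 40 and 2.7 at g = 20. Simulation, which lets the arm sizes vary, gives:

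| Allocation (sites 17/17/16) | SD, gap 40 | SD, gap 20 | P(shift ≥ 10 points), gap 40 | Same, gap 20 |
|---|---|---|---|---|
| Unrestricted | 5.5 | 2.7 | 7.5% | about 0.02% |
| Blocks of 4 | 1.2 | 0.6 | 0 | 0 |
| Blocks of 2, 4, 6 at random | 1.4 | 0.7 | 0 | 0 |

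At a 40-point gap, the alternative site splits give 4.6-5.8 unrestricted (depending on which site carries the gap) against 0.7-1.7 blocked. The contrast does not depend on 17/17/16.

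**4. Against the noise that remains anyway.** Suppose the other two sites have a 30% rate. At a 40-point gap (70% at the third site), p(1 − p) is 0.21 everywhere, so within-site sampling error is √(0.21 × 0.08) = 13.0 points. The total SD is √(13.0² + 5.5²) = 14.1 unrestricted and √(13.0² + 1.2²) ≈ 13.0 blocked. At a 20-point gap the within-site figure is √[(0.34 × 0.25 + 0.66 × 0.21) × 0.08] = 13.4, and the totals are about 13.6 and 13.4.

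**5. What blocks do for 25/25.** Up to three last blocks can be left unfilled. With blocks of 4 the arms differ by at most 2 within a site and 6 overall. Over all three-site splits of 50, exactly 25/25 then occurs in 41-67% of trials and 24 to 26 per arm in at least 88%. With random sizes 2, 4 and 6, the assumed splits give exactly 25/25 in about 44-58%.

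**The case against.** The strongest reply is that Section 7.1 never says the draws are unrestricted. A random number generator can also produce a permuted-block list, and the stated aims fit an intended but undescribed restriction. This stands. A reader might infer that the plan has chosen simple randomization, but the text is silent. What can be shown is that the described procedure, followed literally, does not do what it is said to do.

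Four further replies also stand, and they limit the point.
- **No bias.** A reader might take site imbalance to bias the comparison. Under random allocation it is ordinary chance variation, already reflected in the unadjusted standard error, and it does not inflate type I error.
- **Modest size.** A 30/20 split keeps 4 × 20 × 30/2500 = 96% of the efficiency of 25/25. Step 4 shows a small reduction in total noise, and at a 20-point gap a shift of 10 points almost never happens. Section 2 cites 9% for living wills and 4% for health care proxies among Latinos, so a 40-point gap would be very large for those outcomes.
- **Other aims are not at risk.** It is tempting to say that thematic saturation and the 70% benchmarks need 25 PLAN patients. Section 7 expects saturation at 10, and fewer than 10 in the PLAN arm has a probability of about 3 in a million. The benchmarks are descriptive proportions that do not need a denominator of exactly 25.
- **Pilot.** Section 7 puts feasibility and acceptability first and admits limited power.

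The baseline screen at p < .10 is only a partial answer. It is described as t-tests, which do not suit a three-level site factor, and it brings site in only if site is tested and happens to cross the threshold.

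**Conclusion.** The point holds in a limited form. Section 7.1 claims balance at each site from a method that, as described, restrains nothing, and the outcome models do not include the stratification factor. If the draws are unrestricted, 25/25 is reached in about 11% of trials, and chance site imbalance adds an SD of about 5.5 points (40-point gap) or 2.7 points (20-point gap) to the arm difference, against about 1.2-1.4 or 0.6-0.7 with blocks. The allocation probabilities in step 1 rest only on N = 50 and 1:1 draws. The shift figures rest on assumed site sizes and assumed gaps in background rates, neither of which is in the documents.

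This is a loss of precision in a pilot and does not invalidate the trial. It is still worth correcting, because potential efficacy is part of the primary objective, the results are meant to inform a larger trial, and the remedy costs very little. A reader should not conclude that blocking would deliver exactly 25/25; it bounds the departure from it.

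**What to change.** 1. State in Section 7.1 that allocation is 1:1, stratified by site, using computer-generated permuted blocks of randomly varying size (for example 2, 4 and 6), with each assignment released only after consent and baseline assessment.
2. Describe 25 per arm as a target wherever it appears (Protocol Summary, Sections 3.1, 3.9 and 7).
3. Add site to the outcome comparison in Section 7 as the stratification factor, whatever the baseline screen shows. Where events are rare, use a site-stratified Mantel-Haenszel analysis or a penalized or exact logistic method.

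**Cost.** A new allocation list and a few sentences. Small blocks make some late assignments slightly predictable; varying the sizes and not disclosing them to recruiting staff limits this. Site terms in five ordinary logistic models with 50 patients can cause sparse-data problems: at the 4% health care proxy rate cited in Section 2, 25 control patients would yield about 25 × 0.04 = 1 event. That is the reason for the methods named in item 3.

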3.4 Exclusion Criteria

Patient exclusion criteria: (1) not fluent in English or Spanish; (2) severely cognitively impaired (as measured by Short Portable Mental Status Questionnaire scores of ≥ 6 to be delivered by trained study research staff during screening);⁴¹ (3) too ill or weak to complete the interviews (as judged by interviewer); (4) currently receiving hospice at the time of enrollment (to allow prediction of ACP); (5) children and young adults under age 18; and (6) patients deemed inappropriate for the study by their treating oncologist. Because the primary outcomes include both completion of advance care planning documentation as well as conversations around ACP, we have chosen not to add exclusion criteria around completion of advance directives. The goal of PLAN is two-fold – which is to increase completion of these documents but also to increase engagement in conversations around ACP with loved ones and providers (which can be present or not present despite completion of documents).

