5.1 Schedule of Assessments

Table 1. Schedule of trial events

	Baseline	Post-intervention (with 1 week of completing intervention)	3 mos. after completion of intervention	Off Study
Informed consent	X			
Demographics	X			
Clinical variables				X
Acceptability		X		
Usability		X		
Feasibility		X		
Quality of life	X	X		
Cultural beliefs (Fatalismo, personalismo, respeto)	X	X		
Familial beliefs (Familismo, filial duty)	X	X		
Religious/spiritual beliefs (Religious coping, religious beliefs about end-of-life medical care)	X	X		
Terminal illness acceptance	X	X		
Illness understanding	X	X		
Readiness for ACP	X	X		
Engagement in ACP	X	X		
Healthcare utilization	X	X	X	
Goal-concordant care	X	X	X	

6. Data Reporting / Regulatory Considerations

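### Section 7.1 checks randomization by testing outcomes between arms and names no baseline time point, so as written it repeats the efficacy contrast and cannot assess allocation

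*Combined protocol and SAP*

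**What the plan says.** Section 7.1 (Randomization) describes allocation stratified by site using a random number generator, and then a check. For binary outcomes: "To ensure randomization was effective, separately for each binary outcome, we will perform a two-sample proportions test". For continuous outcomes: "Separately for each continuous outcome, we will perform a two-sample unpaired t-test or unpaired Wilcoxon test". In both cases the question put to the data is whether outcomes differ significantly between the intervention and control groups. The section gives no time point, no significance level and no action to follow a significant result.

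Three statements in section 7 (Statistical Considerations) bear on how to read this:

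- On timing, after participants are randomized: "They will then complete measures of engagement in ACP post-intervention".
- On baseline data, as a separate step that selects covariates at p < .10: "preliminary analyses will utilize t-tests to compare the two groups on baseline characteristics".
- On efficacy: "To test the study aim, five separate logistic regression models will be run in which ACP outcomes" are the dependent variables, with group as the predictor.

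Table 1 (section 5.1) schedules "Readiness for ACP" and engagement in ACP both at baseline and post-intervention. Baseline values of these variables will therefore exist, but section 7.1 does not refer to them.

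**The concern.** Random allocation is what allows a post-intervention difference to be attributed to PLAN. The same difference cannot also serve as evidence that allocation failed. If section 7.1 is followed literally, the trial's hoped-for result and the sign of a failed randomization are one and the same test result.

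Two things are at stake. First, someone applying the stated purpose could read a working intervention as a randomization problem, or read the absence of a difference as reassurance about allocation. Neither inference is valid. Second, ACP readiness, measured with the ACP Engagement Survey, is among the endpoints in the protocol summary (section 1), but section 7 gives no between-arm analysis for any continuous outcome. The only one in the plan is the test in section 7.1, under the label of a randomization check.

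**Working it through.** **1. The plan's own figure.** Section 7.1 states none. The only calculation in section 7 for the same contrast is a sample size of 113 for a "minimum odds ratio of 2.0 for dichotomous outcome measures of ACP", two-sided alpha 0.05, power 0.80. The usual two-proportion formula per arm, with m the mean of p1 and p2, is

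n = [1.96·√(2m(1−m)) + 0.842·√(p1(1−p1) + p2(1−p2))]² / (p1 − p2)².

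Over control rates of 4%, 9%, 20%, 32%, 40% and 50% it gives total N of 1266, 618, 344, 276, 266 and 274. The figure of 113 is not reproduced. That is a separate matter, and nothing below depends on it.

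**2. The check and the efficacy test are the same statistic.** Take 8/25 in control and 16/25 in intervention; the pooled rate is 24/50 = 0.48.

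- Two-proportion test (section 7.1): z² = (0.64 − 0.32)² / (0.48 × 0.52 × 2/25) = 0.1024 / 0.019968 = 5.128, p = 0.024.
- Score test from a logistic model with group only (section 7): U = 16 − 25 × 0.48 = 4; V = 0.48 × 0.52 × 12.5 = 3.12; U²/V = 5.128.

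The match is exact before covariates enter the logistic model.

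**3. How often the check is significant when allocation is perfect.**

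Inputs:
- 25 per arm (section 7).
- Odds ratio 2.0 (section 7).
- Control rates from the background figures for Latinos in section 2: 32% end-of-life discussion, 9% living will, 4% health care proxy.

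Assumptions:
- Two-sided alpha 0.05, because section 7.1 states none.
- The background rates hold in the control arm.
- The single 32% rate applies to both discussion outcomes.
- The DNR rate, which section 2 does not give, lies between 4% and 32%.

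The intervention rate is p2 = p1·OR / (1 − p1 + p1·OR). For example, 0.32 × 2 / (0.68 + 0.64) = 0.485. The probability of significance is the sum, over all pairs of counts from 0 to 25, of the product of the two binomial probabilities wherever the pooled |z| exceeds 1.96.

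| Control rate | No effect | OR 2.0 (intervention rate) | OR 3 | OR 4 | OR 5 |
|---|---|---|---|---|---|
| 32% | 5.4% | 24.7% (48.5%) | 52.1% | 71.2% | 82.5% |
| 9% | 4.5% | 12.8% (16.5%) | 28.1% | 44.6% | 59.2% |
| 4% | 1.2% | 5.0% (7.7%) | 12.9% | 23.1% | 34.0% |

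At 32% against 70%, an odds ratio of (0.70 × 0.68)/(0.30 × 0.32) = 4.96, the figure is 82.1%.

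**4. Any of the five binary outcomes significant.** If the outcomes were independent, the probability is 1 − Π(1 − rate) over 32%, 32%, 9%, 4% and DNR.

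| DNR control rate | No effect | OR 2.0 |
|---|---|---|
| 4% | 16.7% | 55.4% |
| 9% | 19.5% | 59.0% |
| 32% | 20.2% | 64.6% |

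Independence is doubtful, because section 2 reports that a discussion raised the odds of a DNR order tenfold. Under any dependence, the probability is at least the largest single rate: 5.4% with no effect and 24.7% at OR 2.0.

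**5. The baseline reading.** Before treatment there is no effect, so only the no-effect figures apply. With sound allocation each significant result is then a chance finding, which makes a significant baseline difference weak evidence about allocation.

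**The case against.** The strongest reply is that the authors meant baseline values. The stated purpose makes sense only for pre-treatment data, and Table 1 collects readiness and engagement at baseline. This is a fair possibility, and on that reading the main defect is a missing word. But section 7.1 does not say it. Section 7 uses outcomes for the dependent variables of the efficacy models and says baseline when it means baseline. An analyst working from the text would test post-intervention data.

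A second reply is that nothing acts on the result. No alpha, re-randomization rule or covariate rule is attached to these tests; covariates come from the separate p < .10 step; and the five logistic models are clearly assigned to the study aim. This stands. For the binary outcomes the efficacy analysis remains identifiable, and the harm is one of interpretation. It does not help the continuous outcomes, which have no other analysis.

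Third, the percentages are the power of an unadjusted test under assumed rates, and section 7 says that feasibility, acceptability and preliminary data are the main goal. Both points are correct. The figures show that the check responds to efficacy while allocation stays sound; they do not measure damage to the trial. The feasibility and acceptability benchmarks are unaffected.

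**Conclusion.** The concern holds. As written, section 7.1 makes the unadjusted efficacy contrast the test of randomization, and that contrast cannot do the job. With allocation perfect throughout, the chance of a significant result for an outcome with a 32% control rate goes from 5.4% with no effect to 25% at the plan's odds ratio of 2.0 and 82% at 32% against 70%. These figures rest on alpha 0.05, 25 per arm and the background control rates. The conclusion itself rests on the wording and would stand with other rates.

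The part with most consequence is the continuous outcomes: their only between-arm comparison in section 7 is presented as a check on allocation, so its role in judging efficacy is undefined. This should be fixed, but it does not invalidate the trial. The plan contains no explicit rule that would turn a real effect into a declared failure of randomization; that misreading is implied by the stated purpose.

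**What to change.** Remove the outcome tests from section 7.1 as a randomization check and substitute text such as:

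> Baseline characteristics and baseline ACP readiness and engagement will be described by arm and site. Assignments will be verified against the randomization list.

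Describing baseline ACP status by arm is useful here in any case, because section 3.4 states "we have chosen not to add exclusion criteria around completion of advance directives", so some patients may enter with documents already in place.

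If unadjusted outcome comparisons are wanted, move them to section 7 as unadjusted efficacy estimates with confidence intervals. For the binary outcomes, label them secondary to the logistic models. For the continuous outcomes, this gives the only planned comparison its proper role.

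If baseline values were meant all along, say so in section 7.1 and present them descriptively.

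The cost is wording only. No new data or visits are needed, and no planned comparison is lost if the tests are moved. The list of assignments is a product of the site-level random number generation already planned.
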